Typhoid fever is an enteric bacterial infection caused by *Salmonella enterica* serovar Typhi (Salmonella Typhi; S. Typhi). It is an important infectious disease in low- and middle-income countries with over 10.9 million new cases worldwide and 116.8 thousand death in 2017. South Asia and Sub Saharan Africa are the most affected areas of the world. Typhoid fever is common in areas with inadequate sanitation and hyegine. In routine practice, diagnosis of typhoid fever is rarely confirmed as diagnostic tests are unavailable or have limited diagnostic accuracy. Blood culture is the commonest reference standard test but has a lower sensitivity. Alternatives to those methods exist but their performance is poor. The Widal test is still used but as it is based on cross-reactive antigens, it lacks sensitivity and specificity. Clinician often use rapid diagnostic tests to diagnose typhoid. A number of typhoid fever RDTs are commercially available but performance data are not available or not consistent from a study to another. This prospective, multicentre, cross-sectional study will be carried out in 3 hospitals of Nairobi, Kenya. 2000 clinically suspected typhoid cases will be enrolled in this study, blood culture as well as serum for RDT will be received. All typhoid positive and equal typhoid negative serum will be tested for investigational RDTs.

This collaborative study between KEMRI and FIND will systematically compare different point of care typhoid tests currently available in the market against the same set of reference standard. The knowledge gained from this trial may benefit health providers' by providing information on diagnostic accuracy of current typhoid test and to decide on utility of these commercial tests. The result obtained from this trial will also be made available to help inform Ministry of Health in Kenya and the WHO Essential Diagnostic list (EDL) and stakeholder decision making more broadly.

LAY SUMMARY

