This is a prospective multicentre diagnostic accuracy study using collected blood and/or serum samples that will be conducted in three hospitals at Nairobi, Kenya. Participants will be recruited when they present to three hospitals where the study will take place. Clinical officers appointed in the 3 hospitals will collect blood samples from individuals older than eight years presenting with fever because most documented typhoid fever cases involve school-aged children and young adults. The samples will be transported in cold chain to the Centre for Microbiology Research (CMR), KEMRI laboratories where they will be processed using blood culture. Once culture results are available, investigational RDTs will be performed on all blood culture positive and equal culture of negative serum.

Trial Population

The trial population will be composed of adults and children suspected of typhoid between 8-65 years of age because most documented typhoid fever cases involve school-aged children and young adults. Participants will be recruited in 3 hospitals in Nairobi, Kenya.

Inclusion Criteria

Participants are eligible to be included in the Trial only if all of the following inclusion criteria apply:

- Individuals aged 8 years of age to 65 years of age
- History of fever or axillary temperature of >37.5^oCfor at least 3 consecutive days within the last 7 days prior to enrolment
- Clinical suspicion of enteric fever
- One of the following scenarios:
 - Presents to outpatient department or Emergency Department
 - Admitted to hospital within last 12 hours
- Able and willing to provide informed consent (and assent when required)

Exclusion Criteria

Participants are excluded from the Trial if any of the following exclusion criteria apply:

- Unwillingness to participate in the study
- Inability to provide the required volume of blood
- Unwillingness to provide blood
- Known non-infectious / Non typhoid Infectious causes of fever or other alternate diagnosis of fever

Screen Failures

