Trial procedures are summarized in Study flow in Figure 1. Protocol waivers or exemptions are not allowed.

Adherence to the trial design requirements, including those specified in the study flow (Figure 1) is essential and required for trial conduct.

All screening evaluations must be completed and reviewed to confirm that potential participants meet all eligibility criteria. The investigator will maintain a screening log to record details of all participants screened and to confirm eligibility or record reasons for screening failure, as applicable. All enrolled participants will be registered on an enrolment form.

Procedures conducted as part of the participant's routine clinical management and obtained before signing of the Informed Consent Form (ICF) and Informed Assent Form (IAF) may be utilized for screening or baseline purposes provided the procedures met the protocol-specified criteria.

Specimen Collection, Handling, Transport and Storage

[figure not shown]
Procedures for specimen collection, handling, transport, and storage will be described in detail in the Trial Manual provided by FIND to the site. Blood will be collected by venepuncture following national guidelines on drawing blood. The maximum amount of blood collected from each participant in the trial, including any extra assessments that may be required, will not exceed 14 mL. Repeat may be taken at the time of enrolment for safety reasons or for technical issues with the samples. Blood will be handled as follows:

Samples For	Amount of sample in adults	Amount of sample in children
	(>14 years) (14ml- 10+4ml)	(8-14 years) (7ml-3.5+3.5 ml)
Blood Culture	1 x 10 ml whole blood	1 x 3.5 ml whole blood
Serum	1 X 4 ml whole blood	1 X 3 ml whole blood

Table 1: Amount of blood to be collected

Study workflow

The study flow is shown in Figure 1. *Figure 1: Study flow*

Consenting patients will be enrolled in the study based on eligibility criteria. Blood will then be obtained from the patients by venepuncture method. The blood samples will be collected in blood culture bottles and in serum tubes. The volume of blood from the patient will follow the guidelines in **Table 1**. After collection at study hospitals, samples will be transported to the CMR, KEMRI laboratories in cold boxes every day and will be processed within 24 hours maximum. Samples will be stored at 4°C at CMR laboratories until further processing.

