All samples preparations (blood culture and serum preparation) will be conducted in parallel. Blood culture will be done using an automated blood culture system (BD BACTEC 9050). BACTEC vials will be processed as per manufacturer's instructions. Bottles will be incubated until signal-positive or till the end of day 5, whichever is earlier. When positive signal is observed, bottles are unloaded from instrument and Gram's stain and cultures and biochemical tests to identify *Salmonella* Typhi will be performed using standard microbiological procedures. Patients will be classified as typhoid or non-typhoid cases according to the blood culture results. However, since the results of the blood culture may take several days to be available, serum will be separated from all whole blood samples and will be aliquoted. It is expected that at least 100 blood culture positive and 100 blood culture negative samples will be tested with index tests and will be kept for long term storage.

Testing with the index tests will be performed in batch at the end of each month while the remaining volumes of the selected sera will be kept at -80°C. Depending on the initial volume that will differ between adult and children samples, 3 to 6 aliquots will be kept at -80°C for long term storage and will be used for future evaluation of diagnostic tests.

Investigational products

Reference standard tests to identify Salmonella Typhi:

All blood samples collected from study participants will undergo blood culture.

• Blood culture: Blood culture is considered as gold standard for the diagnosis of typhoid fever. Blood culture is a routine process for diagnosis of typhoid fever.

Index tests:

Index tests are RDTs that will be performed according to manufacturer's instructions by trained laboratory personnel. The readers of the index tests and reference standard test will be blinded to the results of the other tests.

Typhoid RDTs for inclusion in the study were selected by the study team based on a combination of the following criteria:

- RDT is CE-marked
- Published independent evaluation data
- International availability
- Volume of samples
- Price of the test
- Turnaround time

RDTs will be procured by FIND and shipped to the study sites in Kenya. There are no financial ties of any nature with the manufacutrers. All selected RDTs which will be included in the study are shown in Table 2.

Table: 2 Lists of RDTs

1	SD Bioline Salmonella Typhi IgG/IgM Fast

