2	Typhidot Rapid IgG/IgM combo test
3	TUBEX TF
4	Typhoid IgG/IgM Combo Rapid Test CE
5	Enterocheck WB
6	Test-it TM Typhoid IgM
7	Typhoid IgG/IgM Rapid Test Cassette
8	S.typhi-S.paratyphi "A" Direct Antigen Detection
9	DiaquickS.typhi IgG/IgM Ab
10	Diaquick S. typhi/paratyphi Ag cassette
11	Widal*

*Widal test is included as index test because it is widely used for decision making of typhoid diagnosis and treatment.

Specificity and sensitivity of only few RDTs are currently available in studies but varies from one study to another and from one geographical region to another. Overall TUBEX test from IDL Biotech has sensitivity of 78% and specificity of 87%, TestTM It from LifeAssay has sensitivity of 69% and specificity of 90%, Typhidot from Reszon Diagnostic has sensitivity of 78% and specificity of 77%.(9) Similarly reported sensitivity and specificity of SD Bioline Salmonella Typhi IgG/IgM from Abbott and Typhoid IgG/IgM Combo rapid test from CTK Biotech are 69%/76% and 40-79%/68-79% respectively. Detail information on each RDTs with package inserts are available.

DATA MANAGEMENT

Data handling and record keeping

All participant data relating to the trial will be recorded in source documents and transcribed on to a paper Case Report Form (CRF) and/or an electronic CRF by trial site staff. Data will then be entered from the paper CRF into FIND's online clinical trials platform (OpenClinica Enterprise Edition *version 4.0*). Data will be verified to ensure they are accurate, correct and consistent with the source documents. CRF will be electronically signed by the study team on site. Data will be cleaned of errors by the study team throughout the trial as it is captured electronically.

Records and documents, including signed ICFs, IAFs (when required) pertaining to the conduct of this trial will be retained by the study team for 5 years after trial completion.

Source Data and Source Documents

Source documents will provide evidence for the existence of the participant and substantiate the integrity of the data collected. The study team will maintain adequate and accurate source documents and trial records that include all pertinent observations on each of the site's trial participants. The study team will request previous medical records or reports (if available). Source documents or certified copies will be filed at the study site.

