The ICF and IAF will contain a separate section that addresses the use of remaining samples for future evaluation studies of typhoid or other febrile illnesses tests. The investigator or authorized designee will explain to each participant the objectives of keeping those samples for future use. Participants will be told that they are free to refuse to participate and may withdraw their consent at any time and for any reason during the storage period.

Benefit/Risk Assessment and Safety Monitoring

The in-vitro diagnostic tests (IVD) under investigation are considered low risk to Trial participants since only venepuncture will be performed. Foreseeable adverse events associated with venepuncture are mild, temporary discomfort at the venepuncture site, bruising, and phlebitis. Very rarely, patients may experience vaso-vagal syndrome during phlebotomy. Vaso-vagal reactions may include diaphoresis, nausea, syncope and rarely fainting.

To minimize adverse events, all phlebotomy will be performed either by study clinical officers trained in phlebotomy, or by trained phlebotomists. In case of adverse event and SAE during phlebotomy, standard medical care will be provided to participants and the treating team as well as investigators will be informed and the event reported to the hospital management, PI and documented in the study record.

Handling and manipulation of pathogenic samples will be performed according to the local biosafety requirements to further minimize risk of contamination for the technical personnel and the environment. Given the nature of the study, termination due to safety or other reasons is not anticipated.

Blood culture is recommended diagnostic test for typhoid fever in Kenya, so the report of blood culture, one of the reference test will be provided to clinician for further clinical management of participants, all other index tests will not be used for the purposes of clinical management, and participants will be treated in accordance with national guidelines. The blood culture results from CMR-KEMRI labs will be available after an average of 5 days and will be sent to the clinician caring the participating patient All participants enrolled in the trial will receive standard-of-care health services from the health facility. All trial activities will be conducted by trained trial personnel.

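### What may inform clinical suspicion at entry is not stated and prior Widal or RDT results are not recorded, so an index test could influence enrolment without the data showing it

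*Combined protocol and SAP*

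**What the plan says.** All references are to the combined protocol and SAP.

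- **Inclusion Criteria.** Besides age, fever, care setting and consent, a participant must meet "Clinical suspicion of enteric fever". What may or may not contribute to the suspicion is not stated. Outpatients, emergency patients and patients admitted within the previous 12 hours are eligible.
- **Trial Procedures.** Routine procedures carried out before consent "may be utilized for screening or baseline purposes provided the procedures met the protocol-specified criteria". No test is named and none is exempted.
- **Opening summary.** "Clinician often use rapid diagnostic tests to diagnose typhoid".
- **Table 2, footnote.** "Widal test is included as index test because it is widely used for decision making of typhoid diagnosis and treatment". Table 2 lists ten RDTs and Widal as index tests.
- **Index tests.** "The readers of the index tests and reference standard test will be blinded to the results of the other tests". This covers the readers, not the clinical officer who enrols.
- **Benefit/Risk Assessment and Safety Monitoring.** Apart from blood culture, "all other index tests will not be used for the purposes of clinical management". This concerns care. It does not address a site's own test done before consent, or the use of its result for eligibility.
- **Appendix 1, clinic case report form.** It records symptoms, illness in the past six months, antibiotics, vaccination and presumed diagnosis. It has no item for a typhoid test already done in the current episode.

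**The concern.** The primary endpoint is the sensitivity and specificity of each index test against blood culture. These are unbiased for the intended population only if, within culture-positive and within culture-negative patients, the chance of enrolment does not depend on the index test result. If a local Widal or RDT result feeds into suspicion, patients with a negative result are less likely to be enrolled. False negatives and true negatives are then under-represented, so apparent sensitivity rises and apparent specificity falls for that test. Another index test shifts only in so far as it agrees with the local test beyond what culture status explains.

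Two features of the plan do not protect against this. The culture negatives selected to match the positives in number come from the same enrolled group. The Wilson interval reflects sampling error only. Without a record of prior testing, an analyst could not separate participants whose entry may have been influenced from the rest.

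**Working it through.** **The plan's own figures.** Sample Size gives 100 culture positives, 5% prevalence, 2,000 enrolled and ±14% with 80% power at an assumed 50%.
- Enrolment: 100 / 0.05 = 2,000.
- Precision: (1.960 + 0.842) × √(0.5 × 0.5 / 100) = 2.802 × 0.05 = 0.140.

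Both reproduce. For scale, the ordinary 95% half-width at n = 100 and 50% is 1.960 × 0.05 = 9.8 points.

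**Inputs for the illustration.**
- Widal accuracy, from Introduction/Background: sensitivity 34% to 57%, specificity 43% to 83%. Pairing the two upper ends and the two lower ends is my assumption.
- f, the fraction of otherwise eligible patients with a local Widal before screening: not in the documents. I take 10%, 30% and 50%.
- Upper-bound assumptions: every patient with a local negative result is not enrolled, the study Widal reproduces the local result exactly, and pre-testing is unrelated to the result.

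**Formulas.** All test positives are enrolled, and test negatives with probability 1 − f. So:
- Apparent Se = Se / [(1 − f) + f·Se]
- Apparent Sp = (1 − f)·Sp / [(1 − f) + f·(1 − Sp)]

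**Example, f = 30%, Se 57%, Sp 83%.**
- Se: 0.57 / (0.70 + 0.171) = 0.57 / 0.871 = 65.4%.
- Sp: 0.70 × 0.83 / (0.70 + 0.051) = 0.581 / 0.751 = 77.4%.

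| f | Start 57% / 83% | Start 34% / 43% |
|---|---|---|
| 10% | 59.6% / 81.5% | 36.4% / 40.4% |
| 30% | 65.4% / 77.4% | 42.4% / 34.6% |
| 50% | 72.6% / 70.9% | 50.7% / 27.4% |

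At f = 10% the bound is a shift of about +2.5 points in sensitivity and −1.5 to −2.6 in specificity. At f = 30% it is about +8.4 and −5.6 to −8.4. At f = 50% it is about +16 to +17 and −12 to −16.

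**Share of participants already tested, f = 30%, 57% / 83%.**
- Culture positives: 0.171 / 0.871 = 19.6%, about 20 of 100.
- Culture negatives: 0.051 / 0.751 = 6.8%, about 7 of 100.
- Leaving out the 20 positives, the plan's precision formula gives 2.802 × √(0.25 / 80) = 15.7%, against 14.0%.

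**Culture yield, f = 30%, starting from 5%.**
- At 57% / 83%: 0.05 × 0.871 / (0.05 × 0.871 + 0.95 × 0.751) = 0.0436 / 0.7570 = 5.8%.
- At 34% / 43%: 0.05 × 0.802 / (0.05 × 0.802 + 0.95 × 0.871) = 0.0401 / 0.8676 = 4.6%.

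Selection of this kind could therefore move the yield either way.

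**The case against.** The best case for the plan is that this bias is possible but not built in. Much of that stands, and it limits what may be concluded.

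- **A reader might infer that the routine-procedures sentence makes a Widal or RDT result a screening criterion.** It does not. The sentence is general and carries a proviso, and no eligibility criterion or checklist item asks for such a result. The gap lies mainly in the inclusion criterion, with this sentence as a secondary opening.
- **A reader might infer that a Widal-negative patient is excluded as having another diagnosis.** That exclusion reads "Known non-infectious / Non typhoid Infectious causes of fever or other alternate diagnosis of fever". A negative Widal identifies no other cause, so it does not meet it.
- **A reader might infer that the three hospitals pre-test.** No section says so. The summary and the Table 2 footnote describe general practice. Some text points the other way: Study Design describes recruiting people who present with fever, Sample Size counts all febrile presentations as available, and Benefit/Risk describes blood culture as the recommended test in Kenya.
- **A reader might infer that the bias could never be detected.** That is too strong. Previous medical records are to be requested where available, and a screening log is kept, so some prior tests could be recovered. Recovery would be incomplete: no field captures the result, and screen failures are defined as people who consented, so a patient never approached need not appear. Figure 1, the study flow, could not be read.
- **A reader might infer that the ranking of tests is distorted in a known direction.** That requires knowing which tests are used locally and how they correlate with the others. The documents give neither.

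Enrolling on clinical suspicion is itself a legitimate way to obtain the intended-use population. What survives the objection is narrower: no text keeps a prior index-test result out of that suspicion, and no form records it.

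**Conclusion.** The gap is real and worth closing as a cheap improvement. The protocol leaves open whether a Widal or RDT result from the current episode may influence entry, and the clinic form does not record one. Any resulting bias in the primary endpoint could not be reliably assessed from the trial data.

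The documents do not show that the bias will occur, and they do not allow its size to be estimated. The tabulated shifts are upper bounds on an assumed f. They shrink if some local negatives are still enrolled or if local and study results disagree, and they vanish if the sites do not pre-test. They apply directly to the test used locally, and to the other index tests only through their correlation with it. A reader who took the 30% row as an expected shift of about 8 points in sensitivity would be going beyond the documents. The sample size does not need to change on this account.

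**What to change.** 1. In the third inclusion criterion, state that suspicion is based on history and examination, and that a Widal or typhoid RDT result from the current episode is used neither to include nor to exclude. Say the same beside the routine-procedures sentence in Trial Procedures. This concerns eligibility only, not which tests clinicians order for care.
2. Add one item to the clinic case report form: whether a Widal or typhoid RDT was already done in this episode, which test, and its result.
3. Keep the planned outcome 1.1 analysis as primary. Add a sensitivity analysis that leaves out participants tested before enrolment, and report how many there were by site.

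**Cost.** A short eligibility clause with its cross-reference, one form item, a line of site training and one extra table. Culture yield may change slightly. The sensitivity analysis loses precision: under the illustrative model at f = 30% and sensitivity 57%, about 20 of 100 culture positives drop out. It also has a limit of its own. If clinicians pre-test a particular kind of patient, the remaining participants are a different mix, so a difference between the two analyses needs cautious reading. The form item covers enrolled participants only; preventing selection depends on the eligibility clause, so both should be in place before screening starts.

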Each enrolled participant will be assigned a unique study participant ID number used to identify samples and information. The use of an anonymous participant ID will ensure participant's confidentiality. To ensure that each clinical sample can be linked to clinical and laboratory results and tracked effectively from the collection site to the end-user, all lab request forms, sample collection pots, tubes and aliquots will be labelled using the participant's ID using a set of barcode labels provided by FIND.

Each set will be composed by the label types, according to the number and type of specimens collected at each site as described in Table 4. Labels will contain readable text and a barcode: *Table 4: Composition of Barcode labels*

Label Type	Content	Text	Barcode	Use
Core label	 Study ID Site ID Participant ID 	Yes	Yes	Place on Information sheet, CRF, enrolment form and lab results form
Specimen label	 Study ID Site ID Participant ID Event ID Specimen type 	Yes	Yes	Place on blood culture bottle and serum tubes
Aliquot label	 Study ID Site ID Participant ID Event ID Specimen type Aliquot ID 	Yes	Yes	Place on tubes containing serum for testing of investigational RDTs and for long-term storage of serum

Data Management procedures, including the setup of the database, programming edit and range checks and querying, are described in the Data Management Plan.

Whenever possible clinical data and laboratory results will be captured directly onto electronic CRFdesigned by FIND/KEMRI in the OpenClinica EDC system. Site staff will be responsible for entering their data from a paper CRF into OpenClinica where direct capture into EDC is not possible. Test results will be exported from the devices when possible and

electronic files will be transferred to FIND for further analysis. FIND will setup a secure data transfer system such as a File Transfer Protocol (FTP) server. Details will be provided in the Trial Manual.

The site will be provided with individual password-protected accounts to access OpenClinica, following a training session given by FIND, either on site or remotely sharing screen through Skype or any other similar system.

No information concerning the trial or the data generated from the trial will be released to any unauthorized third party without prior written approval of the study team.

Statistical Analysis Plan

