BUDGET SUMMART	Unit	Unit Cost	Cost (EUR)
Personal Cost			Cost (LCIK)
Project supervisor (Manager), PhD-KEMRI Staff			8,700
monthly salary: 2900 euros; gratuity:0, period: 9 months			0,700
3 Clinical Officers, Diploma (From Hospitals) - To give 55%			7,920
monthly salary: 440 euros; gratuity: 0			.,
2 Laboratory Technologists, BSc (From KEMRI) - To give 65%			7,800
effort monthly salary: 440 euros; gratuity:0			
Field Driver - KEMRI (70% effort)			5,208
Sub-Total			29,628
Blood Culture/Enrichment media/ reagents for blood samples	(2,400 sam	ples)	. /
Columbia blood agar – 500g pack	5	136.7	683.5
MacCONKEY agar -500g pack	5	136.7	683.5
Sulphur, Indole Motility media – 500g pack	1	122.1	122.1
Urea agar and supplement - 500g [contact] =172.1	1	172.1	172.1
TSI	1	172.1	172.1
Simon citrate – 500g pack	1	122.5	122.5
Glass test tubes	3000	0.3	900
Glass slides and cover slips (100 per unit)	30	25	750
Petri dishes –3500 pcs			1000
Disposable sterile wire loops	20,000	0.21	2310
Cotton wool- 500g pack	10	4.4	44.2
Syringes and needles (10ml) 100pc per unit	60	4	240
Serology antiseras: - Polyvalent	2	215.1	430.2
-Monovalent	10	215.1	2151
Biohazard bags (Red, Yellow, Black) – 50 pcs	48	187	8976
Sharps disposal containers	12	821.45	9857.4
Emersion oil	1	500	500
Aerobic Blood Culture bottles, 3000 pieces,50 pcs per unit =19,200	60	320	19200
Sub-Total			48,315
Consumables for archiving isolates, 600 samples			
Sarstedtet Freezing vials	750	0.25	187.5
10 by 10 freezer boxes	7	21	147
Sub-Total			335
Sample transport and Field trips		•	
Fuel for the field vehicle			1,608
Vehicle service and Maintenance			3,192
Sub-Total			4,800
Miscellaneous		.	•
Office and lab Supplies & materials			6,000
Physical protective Equipment (PPE) for the laboratory			1428
personnel (Gloves, dust coats, face masks and Eye goggles)			
Sub-Total			7,428
Total Cost			90,505

Indirect Cost (15%)	13,575.765
Grand Total	104,081

Budget Justification

Personal Costs:

The Project supervisor (Manager) is the Principal Investigator of the trial, he will supervise and coordinate field and laboratory staff in sampling activities for 9 months.

Three Clinical officers from the sampling sites will be involved in the trial. They are currently working in those sites and part of their time will be dedicated to participant screening, consenting and blood drawing.

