Two full timeLaboratory technologist will be involved in the trial. They are currently working in KEMRI. They will process samples for blood culture, PCR and aliquot the serum for storage. Once the culture report comes they will also perform RDTs in stored samples in batches

A designated KEMRI driver will be responsible for transportation of the staff to study sites and samples from study sites to laboratory at KEMRI.

Blood Culture, Enrichment media and Reagents for Blood sample

Blood culture is one of the reference tests of this study. This includes cost for aerobic blood culture bottles with enrichment media for blood culture. Once the blood culture is positive, cost of biochemical media and reagents to identify Salmonella Typhi is included in this section.

Consumables for archiving isolates:

The consumables for archiving serum samples of 100 blood culture positive and equal number of negative cases, each sample will be stored in 4 freezing vials which will be stored at KEMRI for 5 years. These samples will be used for future evaluation of new typhoid diagnostics.

Sample transport and field trips:

Fund to support daily transport of sample after collection from sites to KEMRI laboratory

Miscellaneous costs:

This includes cost of office and laboratory supplies and personal protective equipment for laboratory staffs.

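### The plan promises that RDT readers are blinded to culture, but as written the same two technologists handle cultures and RDTs under one participant ID, with no stated safeguard

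*Combined protocol and SAP*

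**What the plan says.** **The promise.** The Index tests section under Investigational products says: "The readers of the index tests and reference standard test will be blinded to the results of the other tests". It gives no means of achieving this.

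**Who does the work.** Of the two technologists, the Budget Justification (Personal Costs) says: "They will process samples for blood culture, PCR and aliquot the serum for storage". It continues: "Once the culture report comes they will also perform RDTs in stored samples in batches". The Budget Summary has one laboratory line, "2 Laboratory Technologists, BSc (From KEMRI) - To give 65" per cent effort, and no other laboratory post.

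**Which sera are tested.** Study Design says: "Once culture results are available, investigational RDTs will be performed on all blood culture positive and equal culture of negative serum".

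**How they are labelled.** Under Data Management, "all lab request forms, sample collection pots, tubes and aliquots will be labelled using the participant's ID". Table 4 places the participant ID on the culture bottle, on the serum tube and on the aliquot used for RDTs.

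**When.** The Benefit/Risk section says: "The blood culture results from CMR-KEMRI labs will be available after an average of 5 days and will be sent to the clinician". Study workflow schedules the index tests as a batch at the end of each month.

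**The concern.** The reading of a lateral-flow strip or an agglutination test involves judgement on faint or doubtful results. A reader who knows the culture result may resolve doubt in its favour. In culture-positive sera this turns false negatives into true positives; in culture-negative sera it turns false positives into true negatives. Sensitivity and specificity against culture (primary endpoint 1.1) would then both rise. The Wilson interval does not reflect such a shift, a larger sample does not remove it, and it cannot be corrected at analysis. The results are intended for the Kenyan Ministry of Health and the WHO Essential Diagnostics List, so readers will rely on the blinding statement.

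The exposure runs one way. Cultures are final before the RDTs are run, so culture readers are protected by timing.

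**Working it through.** **1. The plan's own figure.** Sample Size uses 50% sensitivity, a margin of 14 points, 80% power and 95% confidence:

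n = (1.960 + 0.842)² × 0.5 × 0.5 / 0.14² = 7.849 × 0.25 / 0.0196 = 100.1, against 100 stated.

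Enrolment is 100 / 0.05 = 2,000, as stated. Over the six months of sample collection this is 100 / 6, or about 17 positives a month. About 2,000 − 100 = 1,900 participants would be culture negative, of whom 100 / 1,900 = 5.3% are tested.

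**2. Can an RDT reader reach the culture result?** The passages, taken together:

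- *Same people.* Two technologists process cultures and later perform RDTs. No passage divides the tasks between them.
- *Same identifier.* The aliquot on the RDT bench shows the ID that was on the culture bottle. No passage replaces it with a code.
- *Result already on record.* Cultures average 5 days and RDTs wait for the culture report and the month end. Table 3 places laboratory results in a lab notebook or LIMS, which makes look-up possible.
- *Recall.* Each signal-positive bottle is worked by hand (Gram stain, culture, biochemical tests). With about 17 S. Typhi positives a month, remembering some IDs is plausible.
- *Audit trail.* The blood-culture form has a field for the operator's initials. The RDT form has no reader field beside each result, so the form alone could not show that readers were separate.

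No passage closes the route from ID to culture result. None shows that the route would be used.

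**3. Size, as an illustration.** The documents give no rate of biased reading. Assume that a fraction d of reads that disagree with culture drift to agreement. True accuracy a then becomes a + d(1 − a), a shift of d(1 − a).

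- Sensitivity 78% (a value quoted in Sample Size), d = 5%: 0.05 × 22 = 1.1 points.
- Same, d = 10%: 0.10 × 22 = 2.2 points.
- Specificity 87% (quoted for the TUBEX test): 0.05 × 13 = 0.65 and 0.10 × 13 = 1.3 points.

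For scale, the Wilson 95% half-width at p = 0.78, n = 100 is

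1.96 × √(0.78 × 0.22 / 100 + 1.96² / (4 × 100²)) / (1 + 1.96² / 100) = 1.96 × 0.04257 / 1.0384 = 0.080, or 8.0 points.

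At 78% the illustrated shift is thus at most about a quarter of the half-width (2.2 / 8.0).

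**The case against.** The strongest reply is that nothing here contradicts the blinding rule. The rule stands in the protocol body. The other text is a budget justification, which speaks of processing cultures and performing RDTs and does not say who reads either. One technologist could read cultures and the other RDTs, and both passages would be true. The budget text is also loosely drafted: it mentions PCR, which is not a reference or index test in this study. Laboratory work may not be confined to the two posts, since Roles of Investigators gives an investigator laboratory processing. Figure 1 is not reproduced, and Quality Management defers all sample testing procedures to a Laboratory Manual, where a coding step could well sit.

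Most of this stands, and it limits the conclusion. It does not remove the point: the promise has no stated mechanism, and the only staffing described does not secure it.

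A reader might infer more than the documents support:

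- *That selecting sera by culture result unblinds the reader.* It does not. A batch mixes positives and negatives, and the label shows no culture result.
- *That the bias could reach 6 points.* That takes the lowest quoted sensitivity, 40% for one product, with 10% drift (0.10 × 60 = 6.0). The drift rate is an assumption, so this is no estimate.
- *That invalid calls are an easy second route, because invalid results are removed.* The RDT form provides a repeat after an invalid result, and invalid rates are themselves a reported secondary endpoint, so misuse would leave a trace.
- *That cultures with other growth are unclassified.* Study workflow classes patients as typhoid or non-typhoid by culture, and the culture form has a separate S. Typhi field. Only the handling of contaminated cultures is left unstated.

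**Conclusion.** The point holds as a gap between a stated protection and the arrangement described to deliver it. As written, RDT readers could learn culture results by recall or look-up. It does not follow that they will, or that the study lacks a safeguard in documents not available here.

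If reading bias occurred, it would be expected to move sensitivity and specificity upwards together. Its size is unknown; 1.1 to 2.2 points at 78% sensitivity rests wholly on the assumed 5-10% drift and is smaller than sampling error at n=100. This is a low-cost improvement, to be made before the first monthly batch, and not a flaw that invalidates the design. Confidence is medium, because a Laboratory Manual with a coding step would reduce it to one missing sentence in the protocol.

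**What to change.** Reconcile the Index tests section with the Budget Justification by stating who reads cultures, who reads RDTs, and how the RDT reader is kept from the culture result. Then, for each monthly batch:

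1. Test all culture positives, as Study Design states. Draw an equal number of negatives at random, with a recorded seed, from that month's final negative cultures. Exclude contaminated cultures; count other growth as non-typhoid, as the plan already implies.
2. A person confirmed not to read RDTs covers the participant ID on the selected aliquots with a blind code and shuffles positives and negatives together. FIND data management holds the key. The project supervisor, of whom the budget text says "he will supervise and coordinate field and laboratory staff in sampling activities for 9 months", is a possible coder only if confirmed to have no part in reading RDTs.
3. Record RDT results, including invalid calls and repeats, under the code with the reader's initials, and lock them before the key is opened.

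Do not add a minimum serum volume for entry to the batch. It would conflict with testing all positives, discard partial results that the MITT set keeps, and could take positives below the expected 2,000 × 5% = 100.

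**Cost.** About 200 extra labels, two fields on the RDT form (blind code and reader initials), and a short monthly task covering about 17 positives and 17 negatives. No extra participants or blood are needed. The initials partly overlap with the existing rule that source data entered directly in the CRF are signed by whoever generated them. Coding adds a small risk of mislinkage, handled by checking the codes against the key. If the Laboratory Manual already contains these steps, a sentence in the protocol citing it is enough.
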